### **6.2.3. Analysis Methods**

The main analysis method of categorical efficacy variables and health outcomes variables will use a logistic regression analysis with region, baseline disease severity (IGA), baseline value and treatment group in the model, except for the analysis on IGA. For IGA, the logistic regression model will include region, baseline disease severity (IGA), and treatment group. Firth's correction will be used in order to accommodate (potential) sparse response rates. The p-value for the odds ratio from the logistic regression model will be used for statistical inference, unless Firth's correction still results in quasi-separation. In that case, Fisher's exact test will be used for statistical inference. The difference in percentages and 100(1-alpha)% CI of the difference in percentages using the Newcombe-Wilson method without continuity correction will be reported. The p-value from the Fisher's exact test will also be produced as a secondary analysis.

The main analysis method for all continuous efficacy and health outcomes variables will use mixed model repeated measures (MMRM) analysis. The MMRM model will use a restricted maximum likelihood (REML) estimation. The model will include treatment, region, baseline disease severity (IGA), visit, and treatment-by-visit-interaction as fixed categorical effects and baseline and baseline-by-visit-interaction as fixed continuous effects. For daily diary assessments, the model for analyses up to Week 16 will include all weekly assessments. An unstructured (co)variance structure will be used to model the between- and within-patient errors. If this analysis fails to converge, the heterogeneous autoregressive [ARH(1)], followed by the heterogeneous compound symmetry (CSH), followed by the heterogeneous Toeplitz (TOEPH), followed by autoregressive [AR(1)], followed by compound symmetry (CS) will be used. The

Kenward-Roger method will be used to estimate the degrees of freedom. Treatment least squares means (LSM) will be estimated within the framework of the MMRM using type 3 sums of squares. Differences in LSM between each dose of baricitinib and placebo (and associated p-values, standard errors and 95% CI) will be used for statistical inference. The LSM difference, standard error, p-value and 95% CI will be reported.

Treatment comparisons for continuous efficacy and health outcomes variables may also be made using analysis of covariance (ANCOVA) for primary and key secondary objectives. When an ANCOVA model is used, the model includes region, baseline disease severity, treatment group, and baseline value. Treatment LSM will be estimated within the framework of the ANCOVA using type 3 sums of squares. Reported differences in LSM and associated p-values, standard errors and 95% CI will be used for statistical inference. Treatment-by-region interaction will also be added to the model for sensitivity purposes and is discussed in Section 6.5.

Beginning on Day 14 a Cox proportional hazard (CPH) model of time (in days) to first observance of a 4-point itch reduction with effects for treatment, region, baseline mean itch, and disease severity will be used to test for treatment differences from placebo. For this analysis, daily itch scores will be compared to the baseline to determine if a 4-point itch reduction has been achieved in patients with a baseline itch of at least 4. The baseline for Itch NRS is defined in Section 6.2.2. Beginning on Day 14, the day on which the first time itch NRS is reduced by at least 4 will be modeled. If any significant difference between any baricitinib dose and placebo is observed then the same analyses will be run on Day 13. This process of evaluating at the next lowest day will proceed until no significant differences are observed. No adjustments for multiple tests and multiple comparisons will be used. This analysis uses the Primary Censoring Rule for patients who are rescued or permanently discontinue study drug (see Section 6.4). Missing daily itch data will be replaced using NRI rule which means missing data is replaced with a non-response which would entail replacing missing values with a time to event of >14 days, censored; >13 days, censored, etc., depending on the window being used. If the model assumptions for the CPH model do not hold, a log-rank test will be used.

Restricted mean survival time will be evaluated at Days 2, 3, 4 and 5 as an exploratory analysis. The model will include terms for baseline disease severity (IGA), baseline itch, region, and treatment group.

Fisher's exact test will be used to test for differences between each baricitinib dose and placebo in proportions of patients experiencing adverse events (AEs), discontinuation from study drug, and for other categorical safety data. Continuous vital signs, body weight, and other continuous safety variables, including laboratory variables will be analyzed by an ANCOVA with treatment group and baseline value in the model. The significance of within-treatment group changes from baseline will be evaluated by testing whether or not the treatment group LSM changes from baseline are different from zero; the standard error for the LSM change will also be displayed. Differences in LSM will be displayed, with the p-value associated with the LSM comparison to placebo and a 95% CI on the LSM difference also provided. In addition to the LSMs for each group, the within-group p-value for the change from baseline will be displayed.

Confusion table will be used to calculate the proportions of responder patients defined at week 16, and at any time between Weeks 8 and 16, for those with improvement on itch NRS or IGA at early week. The confusion table will generate the Positive Prediction Value (PPV) and Negative Prediction Value (NPV), which can assess the performance of predicting late week responders using early week data. All missing values will be treated by NRI method.

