6.1. Inclusion Criteria

Informed Consent

- [1] are at least 18 years of age at the time of informed consent.

Note: Use local requirements to provide consent if the age of adulthood is defined as >18 years

- [2] are able to read, understand, and give documented (electronic or paper signature) informed consent.

Type of Patient and Disease Characteristics

- [3] have a diagnosis of AD at least 12 months prior to screening, as defined by the American Academy of Dermatology: Guidelines of care for the management of AD; Section 1. Diagnosis and assessment of atopic dermatitis ([Appendix 7](#)).
- [4] have moderate to severe AD, including all of the following:
 - a. Eczema Area and Severity Index (EASI) score ≥ 16 at screening (Visit 1) and at randomization (Visit 2)
 - b. IGA score of ≥ 3 at screening (Visit 1) and at randomization (Visit 2)
 - c. $\geq 10\%$ of BSA involvement at screening (Visit 1) and at randomization (Visit 2).
- [5] have a documented history by a physician and/or investigator of inadequate response to existing topical medications within 6 months preceding screening as defined by at least 1 of the following:
 - a. inability to achieve good disease control defined as mild disease or better (e.g., IGA ≤ 2) after use of at least a moderate potency TCS for at least 4 weeks, or for the maximum duration recommended by the product prescribing information (e.g., 14 days for super-potent TCS), whichever is shorter. Topical corticosteroids may be used with or without TCNIs.

- b. Patients who failed systemic therapies intended to treat AD within 6 months preceding screening, such as cyclosporine, methotrexate, azathioprine, and mycophenolate mofetil will also be considered as a surrogate for having inadequate response to topical therapy.
- [6] agree to discontinue use of the following excluded medications/treatments for at least 4 weeks prior to randomization (Visit 2) and throughout the study:
- a. oral systemic corticosteroids
 - b. systemic immunomodulators, including, but not limited to, cyclosporine, methotrexate, mycophenolate mofetil, and azathioprine
 - c. any other systemic therapy used to treat AD or symptoms of AD (approved or off-label use)
- [7] agree to discontinue the use of following excluded medications for at least 2 weeks prior to randomization (Visit 2):
- a. TCS or topical immune modulators (e.g., tacrolimus or pimecrolimus)
 - b. Topical phosphodiesterase type 4 (PDE-4) inhibitor (crisaborole)

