7.2. Method of Treatment Assignment

Patients who meet all criteria for enrollment will be randomized in a 1:1:1 ratio (placebo: baricitinib 2-mg: baricitinib 4-mg) to double-blind treatment at Visit 2 (Week 0).

Randomization will be stratified by geographic region (Europe, Japan, rest-of-world) and disease severity at baseline (IGA 3 vs. 4). Assignment to treatment groups will be determined by a computer-generated random sequence using an IWRS. The IWRS will be used to assign

packages containing double-blind investigational product tablets to each patient according to the study schedule of activities. Site personnel will confirm that they have located the correct packages by entering a confirmation number found on the packages into the IWRS.

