10.1. Sample Size Determination

Study JAIY will aim to enroll approximately 300 patients ≥ 18 years of age. The proposed sample size will ensure an 89% power to detect an absolute difference of 20% between the baricitinib 4-mg and placebo treatment groups and the baricitinib 2-mg and placebo treatment groups, each using a 2-sided alpha of 0.025 and a Fisher exact test, assuming a 10% placebo response rate for the primary endpoint. The assumptions are based on what was observed in the Phase 2 study (JAHG). The proposed end point of IGA 0 or 1 represents patients whose AD is clear or almost clear from a baseline of moderate or severe disease. The anticipated effect size represents 3 times more patients achieving this benefit compared to placebo, which, in discussion with therapeutic experts, is of a magnitude that is considered clinically relevant.

Sample size and power estimates were obtained from nQuery[®] Advisor 7.0.

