10.3.3. Efficacy Analyses

10.3.3.1. Primary Analyses

The primary efficacy measure is the binary outcome of response defined as IGA score of 0 or 1 (clear or almost clear skin) and ≥ 2 -point improvement from baseline at Week 16. Primary analysis will be conducted using a logistic regression as described above with treatment and the stratification variables (disease severity and region) in the model. Nonresponder imputation for missing data as described above will be used.

Additional analysis of the primary efficacy outcome will include analyzing the outcome as observed, that is, whether or not rescue medication was used.

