10.3.3.2. Secondary Analyses

The following secondary categorical outcomes will be analyzed in a similar manner as the primary; that is, using the same logistic regression model, but with respective baseline scores as further covariate included. Nonresponder imputation will be used for these analyses unless otherwise noted.

- EASI75 at Week 16. EASI75 is defined as having an improvement of at least 75% from baseline. Besides NRI, this outcome will also be analyzed using observed cases, that is, whether rescue medication was given or not.
- EASI90 at Week 16. EASI90 is defined as having an improvement of at least 90% from baseline.
- SCORAD75 at Week 16. SCORAD75 is defined as having an improvement of at least 75% from baseline.
- SCORAD90 at Week 16. SCORAD90 is defined as having an improvement of at least 90% from baseline.
- 4-point improvement in Itch NRS at 1 week, 2 weeks, 4 weeks, and 16 weeks.

The following continuous measures will be analyzed with the MMRM model described above unless otherwise noted. Contrasts within the MMRM model will be used to assess treatment differences for time points of interest as specified above in the list of objectives.

- Mean change from baseline in the following outcome measures:
 - ADSS Item 2 score
 - EASI score
 - SCORAD score
 - BSA
 - Itch NRS
 - POEM total score
 - PGI-S-AD
 - HADS
 - DLQI total score
 - WPAI (4 domains)
 - EQ-5D-5L (VAS, health state index)
 - PIQ – General
 - PIQ – Activity and Clothing
 - PIQ – Mood and Sleep
 - PIQ – Scratching Behavior
 - PROMIS – Sleep-Related Impairment
 - Neuro-QoL - Cognitive Function
 - Patient Benefit Index.

The EASI total score and SCORAD total score will also be analyzed as observed, that is, not assuming missing values after rescue medication is given.

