### 6.3. Covariate Adjustment

The randomization to treatment groups at Week 0 (Visit 2) is stratified by disease severity (IGA) and geographic region as described in Section 5.1. Unless otherwise specified, the statistical analysis models will adjust for these stratification variables. The covariates used in the logistic model for categorical data will include the parameter value at baseline. The covariates used in the ANCOVA model for continuous data will include the parameter value at baseline. Inclusion of baseline in the model ensures treatment LSM are estimated at the same baseline value. When an MMRM analysis is performed, baseline value and baseline-by-visit interactions will be included as covariates.

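### Baseline EASI, already collected on every patient, could be added to the primary IGA (0,1) logistic model as a free gain in power

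*SAP*

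**What the plan says.** SAP 6.2.3 sets the model for IGA endpoints: "For IGA, the logistic regression model will include region, baseline disease severity (IGA), and treatment group". Firth's correction is applied, and the p-value for the odds ratio is the basis for inference. Protocol 10.3.3.1 agrees: the primary analysis is a logistic regression "with treatment and the stratification variables (disease severity and region) in the model".

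For the secondary categorical outcomes, Protocol 10.3.3.2 plans an analysis "using the same logistic regression model, but with respective baseline scores as further covariate included". SAP 6.3 gives the general rule: "The covariates used in the logistic model for categorical data will include the parameter value at baseline". The EASI75 and EASI90 models therefore contain baseline EASI next to region and the IGA stratum.

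Inclusion criterion 4 (Protocol 6.1) requires, at both Visit 1 and Visit 2, an IGA of 3 or more on a scale that ends at 4 and an EASI of 16 or more on a scale that ends at 72. Baseline IGA is thus the same two-level variable as the severity stratum. Baseline EASI should be available for essentially every randomised patient.

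The treatment difference in percentages is reported with an unadjusted Newcombe-Wilson interval (SAP 6.2.3).

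**The concern.** The primary test uses a coarse measure of baseline severity when a finer one is in hand. According to Protocol 9.1.1 and 9.1.2.1, IGA and EASI share three clinical signs (erythema, papulation/induration and lichenification), and EASI also grades excoriation and extent over four body regions. Two patients with IGA 4 may have quite different EASI scores, and the one with more disease may be less likely to become clear or almost clear. If so, a primary model without EASI gives up some power for both dose comparisons. Recovering it would need no further patients or data.

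**Working it through.** **Inputs.** 100 patients per arm (Protocol 5.1). Placebo response 10%, difference 20 points, hence 30% on baricitinib; planned test "each using a 2-sided alpha of 0.025 and a Fisher exact test, assuming a 10% placebo response rate for the primary endpoint" (Protocol 10.1). Model: Firth logistic regression with region, IGA stratum and treatment (SAP 6.2.3).

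**The plan's own figure.** Exact enumeration of the two-sided Fisher test over two Binomial(100) arms at 10% and 30%, alpha 0.025, gives power 0.8913. The stated 89% reproduces.

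**Adding EASI.** Trials were simulated from

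logit P(response) = a + t·(treatment) + b·(IGA 4) + region effect + g·(EASI in SD units within IGA stratum),

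with a and t solved so that the marginal rates stay at 10% and 30% for each g. Each trial was analysed by Firth logistic regression with a Wald test at two-sided 0.025, once with the planned covariates and once with baseline EASI added.

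The value of g is not in the documents, so a range is shown. Other assumptions: 45% of patients with IGA 4, b = −0.7, region log odds 0, 0.3 and −0.2, mean EASI 1 SD higher in IGA 4. There were 4,000 trials per row, with a Monte Carlo error of about 0.45 points on each power.

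| g (odds ratio per SD) | Power, planned model | Power, with EASI | Change (points) | Mean log odds ratio for treatment | Mean SE |
|---|---|---|---|---|---|
| 0 (1.00) | 91.2% | 91.1% | −0.1 | 1.388 → 1.388 | 0.410 → 0.411 |
| −0.25 (0.78) | 90.7% | 90.8% | +0.1 | 1.374 → 1.386 | 0.409 → 0.412 |
| −0.50 (0.61) | 91.3% | 91.4% | +0.1 | 1.374 → 1.425 | 0.410 → 0.420 |
| −0.75 (0.47) | 90.7% | 92.6% | +1.9 | 1.378 → 1.493 | 0.410 → 0.432 |
| −1.00 (0.37) | 91.2% | 93.8% | +2.6 | 1.374 → 1.576 | 0.409 → 0.447 |

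**Mechanism.** The standard error rises in every row. The test gains because the conditional log odds ratio grows faster. In the last row the ratio of estimate to SE goes from 1.374/0.409 = 3.36 to 1.576/0.447 = 3.53, about 5% higher. In the first row it is 1.388/0.410 = 3.39 against 1.388/0.411 = 3.38, so an uninformative covariate costs almost nothing.

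**Robustness.** Two further sets of paired simulations of the same Firth analysis, at 100 per arm and alpha 0.025, gave these changes in power:

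| Size of log odds ratio per SD | 10% vs 30% | 10% vs 25% |
|---|---|---|
| 0 | −0.2 and 0.0 | −0.5 and +0.1 |
| 0.5 | +0.2 and +0.7 | +1.5 and +1.1 |
| 0.8 | +1.9 and +2.4 | +3.5 and +3.9 |
| 1.0 | +3.3 and +3.6 | +4.6 and +4.1 |

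The 10% vs 25% column is not the planning scenario. It shows what happens if the true effect is smaller than planned; in one of these sets, power under the planned model there was only about 69 to 70%.

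**The case against.** The strongest case against is that the plan is coherent as it stands. Each logistic model carries the stratification factors and its own endpoint's baseline value. For IGA those coincide, so a separate baseline term would be redundant, and that explains the exception in SAP 6.2.3. No other endpoint borrows the baseline score of a different instrument, apart from the IGA stratum. Planned power is met without EASI, and the prognostic strength of EASI within an IGA stratum is an assumption. All of this stands, and it is why the point is a suggestion for efficiency and not a correction.

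A reader might infer four stronger things, none of which the documents support:

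- **That the IGA model is inconsistent with the rest of the SAP.** It is not; it follows the rule in SAP 6.3.
- **That it is the only categorical model without a continuous baseline score.** The exception also covers IGA 0/1 at Week 4 and IGA 0 at Week 16. The Patient Benefit Index responder analysis has no ordinary baseline score, and skin infections use Fisher's exact test.
- **That precision is lost.** In logistic regression the standard error rises when EASI is added. What may be lost is power.
- **That the primary hypotheses gate every key secondary claim.** The text of SAP 6.6 lists the hypotheses, but the order and the passing of alpha are in Figure JAIY.6.1, which was not available to this review, so this cannot be confirmed.

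The objection that the change alters the estimated quantity is also correct. The odds ratio would condition on EASI as well as on region and IGA stratum. The unadjusted risk difference and its interval would be untouched.

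**Conclusion.** This is a free improvement, not an error. The primary IGA model is valid and internally consistent, and it has about 91% power under the planning assumptions against the 89% stated.

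Adding baseline EASI leaves power essentially unchanged if EASI says little beyond the IGA stratum. At 10% vs 30% it adds roughly 2 to 4 points if EASI is strongly prognostic (log odds ratio about 0.8 to 1.0 per SD within stratum). At a moderate 0.5 per SD the gain is below 1 point. If the true effect were 15 points (10% vs 25%), the gain at the strong end would be about 3.5 to 4.6 points.

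These sizes rest on the assumed prognostic strength, on an effect of EASI linear on the logit scale, on 100 patients per arm, and on alpha 0.025 per dose as in the sample-size section. The case for the change is its asymmetry: almost no cost if EASI is uninformative, and a modest gain in the primary test if it is informative.

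**What to change.** Before unblinding, state in SAP 6.2.3 and 6.12.1 that the logistic model for IGA (0,1) includes baseline EASI as a continuous covariate, for both dose comparisons, next to region, baseline IGA and treatment. Align Protocol 10.3.3.1 and the general model descriptions in the protocol synopsis and 10.3.1. Keep the currently planned model as a prespecified sensitivity analysis, and note that the primary odds ratio is now also conditional on baseline EASI. If the sponsor prefers the current model, a sentence giving the reason would be enough.

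The change needs no patients, visits or data, and baseline EASI is already used in the EASI75 model. It does need a further SAP version, since Version 2 is recorded as approved. The logistic models behind the placebo multiple imputation, tipping point, region-interaction and subgroup analyses should be checked for consistency. Under Protocol 10.3.1 the sponsor must also decide whether the primary model is a principal feature that calls for a protocol amendment. The covariate has to be fixed before unblinding, because choosing it afterwards would not be credible.

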### 4.3. Exploratory Objectives

The exploratory objectives of this study are the following:

Objectives/Endpoints

 
• Frequency of patient-reported “no itch” (Itch NRS score = 0) days from daily diaries from Week 0 to Week 16
 
• Frequency of patient-reported “no pain” (Skin Pain NRS score = 0) days from daily diaries from Week 0 to Week 16
 
• Mean change from baseline in PIQ – Itch Interference score
 
• Mean change from baseline in PIQ – Activity and Clothing score
 
• Mean change from baseline in PIQ – Mood and Sleep score
 
• Mean change from baseline in PIQ – Scratching Behavior score
 
• Mean change from baseline in PROMIS – Sleep-Related Impairment score
 
• Mean change from baseline in Neuro-QoL – Cognitive Function score
 
• Patient Benefit Index score at 16 weeks – global score plus the following subscales: 
 
○ Reducing social impairments
 
○ Reducing psychological impairments
 
○ Reducing impairments due to therapy
 
○ Reducing physical impairments
 
○ Having confidence in healing
 
 
 
• Proportion of patients achieving PBI global score <math>\geq 1</math> at 16 weeks
 
• Mean change from baseline in the score of Item 1 of the ADSS at 1 week and 16 weeks
 
• Proportion of patients achieving a <math>\geq 1</math>-point improvement in the score of Item 1 of the ADSS for those with baseline Item 1 score <math>\geq 1</math>
 
• Proportion of patients achieving a <math>\geq 1</math>-point improvement in the score of Item 2 of the ADSS for those with baseline Item 2 score <math>\geq 1</math>
 
• Proportion of patients achieving a <math>\geq 2</math>-point improvement in the score of Item 2 of the ADSS for those with baseline Item 2 score <math>\geq 2</math>
 
• Mean change from baseline in the score of Item 3 of the ADSS at 1 week and 16 weeks
 
• Proportion of patients achieving a <math>\geq 1</math>-point improvement in the score of Item 3 of the ADSS for those with baseline Item 3 score <math>\geq 1</math>
 
• To evaluate changes from baseline in immunoglobulin E levels during the study
 
• To evaluate changes from baseline in eosinophil levels during the study
 
• To assess time to 4-point Itch NRS improvement during the first 14 days after initiation of treatment
 
• To assess time to 4-point improvement in Skin Pain during the first 14 days after the initiation of treatment
 
• Proportion of patients achieving a <math>\geq 4</math>-point improvement in DLQI total score for those with baseline DLQI total score <math>\geq 4</math>
 
• Proportion of patients achieving DLQI total score 0 or 1
 
• Proportion of patients achieving a <math>\geq 4</math>-point improvement in POEM total score for those with baseline total score <math>\geq 4</math>
 
• Proportion of patients achieving HADS Anxiety Score <math>< 8</math> for those with baseline HADS Anxiety Score <math>\geq 8</math>
 
• Proportion of patients achieving HADS Depression Score <math>< 8</math> for those with baseline HADS Depression Score <math>\geq 8</math>
 
• Proportion of patients achieving improvement with HADS Anxiety Score or HADS Depression Score <math>< 8</math> for those with baseline HADS Anxiety Score <math>\geq 8</math> or HADS Depression Score <math>\geq 8</math>
 
• Mean change from baseline in HADS subscale scores
 

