## 5. Study Design

### 5.1. Summary of Study Design

[figure not shown]
Study I4V-MC-JAIY (JAIY) is a Phase 3, multicenter, randomized, double-blind, placebo-controlled, parallel-group, outpatient study evaluating the efficacy and safety of baricitinib 2 mg QD and 4 mg QD, in combination with TCS, as compared to placebo in combination with TCS, in adult patients with moderate to severe AD. The study is divided into 3 periods, a 5-week Screening period, a 16-week Double-Blinded Treatment period, and a 4-week Post-Treatment Follow-Up period. For those patients who complete the 16-week treatment period, there is an option to participate in the long-term extension study I4V-MC-JAHN (JAHN).

Approximately 300 patients  $\geq 18$  years of age who have responded inadequately to topical therapy will be randomized at a 1:1:1 ratio to receive placebo QD, baricitinib 2 mg QD, or baricitinib 4 mg QD in combination with TCS (100 patients in each treatment group). Patients will be stratified at randomization according to disease severity (Investigator's Global Assessment [IGA] 3 vs. 4) and geographic region.

Study JAIY will consist of 3 periods:

- Period 1: Screening period is between 8 and 35 days prior to Week 0 (Visit 2)
- Period 2: Double-Blind, Placebo-Controlled Treatment period from Week 0 (Visit 2) through Week 16 (Visit 8)
- Period 3: Post-Treatment Follow-Up period from last treatment visit at Week 16 (Visit 8) or Early Termination Visit (ETV) to approximately 28 days after the last dose of investigational product

Figure JAIY.5.1 illustrates the study design. The blinding procedure is described in the Protocol.

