### 6.2. General Considerations

This plan describes *a priori* statistical analyses for efficacy, health outcomes, and safety that will be performed.

Statistical analysis of this study will be the responsibility of Eli Lilly and Company (Lilly). The statistical analyses will be performed using SAS® Version 9.4 or higher.

Not all displays described in this SAP will necessarily be included in the clinical study report (CSR). Not all displays will necessarily be created as a "static" display. Some may be incorporated into interactive display tools instead of or in addition to a static display. Any display described in this SAP and not included in the CSR will be available upon request.

Statistical tests of treatment effects and confidence intervals (CIs) will be performed at a 2-sided significance level of 0.05, unless otherwise stated (e.g., graphical multiple testing strategy in Section 6.6).

Data collected at ETVs will be mapped to the closest scheduled visit number for that patient if it falls within the visit window as discussed in Section 6.2.2. For by-visit summaries, only visits in which a measure was scheduled to be collected will be summarized. Any unscheduled visit data will be included at the patient-level listings. However, the data will still be used in other analyses, including shift analyses for safety analytes, change from baseline using modified last observation carried forward (mLOCF) for efficacy analyses, and other categorical analyses including safety.

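### In the exploratory time-to-itch-relief step-down, either dose's significance keeps both doses under test, so an ineffective dose can show a false early significant day more often than 5%

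*SAP*

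**What the plan says.** SAP 4.3 lists the question among the exploratory objectives: "To assess time to 4-point Itch NRS improvement during the first 14 days after initiation of treatment".

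SAP 6.2.3 gives the method. It is introduced as "Beginning on Day 14 a Cox proportional hazard (CPH) model of time (in days) to first observance of a 4-point itch reduction", with the comparison to baseline made "in patients with a baseline itch of at least 4". A log-rank test replaces the Cox model if the model's assumptions fail. The rule for moving to an earlier day is: "If any significant difference between any baricitinib dose and placebo is observed then the same analyses will be run on Day 13". It then continues: "This process of evaluating at the next lowest day will proceed until no significant differences are observed". On error control the section is explicit: "No adjustments for multiple tests and multiple comparisons will be used". No separate level is given, so the default in SAP 6.2 applies: "Statistical tests of treatment effects and confidence intervals (CIs) will be performed at a 2-sided significance level of 0.05, unless otherwise stated".

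No sentence ends testing of a dose at that dose's own first non-significant day.

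**The concern.** Stepping back through time and stopping at the first non-significant day is a sound device when each hypothesis is gated by its own preceding result. A dose with no effect must first be falsely significant at Day 14 before any earlier day is examined, so its chance of any false significant day is the Day 14 error rate, about 5%.

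Here the gate asks only whether at least one dose differs from placebo. If 4 mg works and 2 mg does not, 4 mg holds the gate open while 2 mg is tested again on Day 13, Day 12 and so on, whatever it showed at Day 14. The same happens with the doses reversed.

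At stake is the interpretation of early itch relief for the weaker dose. Protocol 3.2 says the study will add information on the timing of the effect on itch, and walking back one day at a time has little purpose other than to find how early the arms separate.

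**Working it through.** **Stated figure.** The SAP gives no error rate for this step-down, so there is none to reproduce. The benchmark is the nominal two-sided 0.05 per test.

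**Inputs from the documents**
- Level of each daily test: 0.05, two-sided (SAP 6.2).
- Gate: either dose significant; both comparisons are then rerun (SAP 6.2.3).
- Stop: when neither dose is significant, so at most 14 tests per dose, Days 14 to 1.
- Multiplicity adjustment: none (SAP 6.2.3).
- Arm size: "100 patients in each treatment group" (SAP 5.1). The number with baseline itch of at least 4 is not given.

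**Assumptions, not in the documents**
- 90 or 100 analysable patients per arm.
- Placebo response by Day 14 of 10% to 40%.
- Hazard ratio (HR) of the effective dose against placebo from 1 to 5.
- Event-time shape from decreasing to increasing hazard (Weibull shape 0.7 to 1.5).
- The other dose identical to placebo.

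**Step 1: what the gate does.** Let Z(k) be the null dose's test statistic on data truncated at Day k.
- Own gate: P(any false day) = P(|Z(14)| > 1.96), about 5%.
- Shared gate: P(any false day) = P(|Z(k)| > 1.96 for some tested k), where the number of tested days depends largely on the other dose.

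**Step 2: limiting case.** Treating the 14 tests as independent would give 1 − 0.95^14 = 51%. That is wrong here, because the data are cumulative and the tests strongly correlated. With equal information added each day, the chance of at least one false significant day is 6.3% over the last 2 days, 11.2% over 7 and 22.0% over all 14. Of that 22.0%, 11.1 points favour the drug.

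**Step 3: the full step-down, log-rank.** 40,000 simulated trials per cell, 100 per arm, constant hazard. Entries are the chance that the null dose shows at least one significant day.

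| Placebo response by Day 14 | HR 1 | HR 2 | HR 3 | HR 4 | HR 5 |
|---|---|---|---|---|---|
| 10% | 5.3% | 8.2% | 12.2% | 14.7% | 16.1% |
| 20% | 5.5% | 10.6% | 16.8% | 18.9% | 19.5% |
| 30% | 5.5% | 13.0% | 18.9% | 20.2% | 20.3% |
| 40% | 5.5% | 14.7% | 19.8% | 20.8% | 20.8% |

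Varying the hazard shape and arm size widens the range for HR 3 to 5 to about 12% to 22%.

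To place these hazard ratios on the response scale, HR = ln(1 − active rate) / ln(1 − placebo rate). A rate of 50% against 20% is 0.693/0.223 = 3.1; 60% against 20% is 0.916/0.223 = 4.1.

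**Step 4: Cox Wald test** (three arms, no covariates; conservative when early events are few).
- HR 3, placebo 20% to 40%: 11% to 15%.
- HR 5, placebo 20% to 40%: 12.5% to 15%.
- HR 3 to 5, placebo 10%: 7% to 9%.
- HR 2: 5% to 12%.

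**Step 5: direction.** With placebo 20% to 40% and HR 3 to 5, false days favouring the drug occur in 6% to 11% of trials, against a nominal 2.5%.

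**Step 6: dose-specific gate.** In every scenario the null dose's rate returns to 4.8% to 5.2%.

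**The case against.** The strongest reply is that nothing confirmatory is touched. The objective is exploratory, the lack of adjustment is stated beside the rule, and SAP 6.6 confines multiplicity control to the primary and key secondary endpoints. Four-point itch response at Day 2 and Weeks 1, 2, 4 and 16 is tested for each dose inside the graphical procedure, so a formal early-itch conclusion does not depend on this analysis. All of that stands. A reader might infer that the trial's type I error is inflated; the documents do not support it.

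A reader might also infer that the SAP will report a day of onset for each dose. It does not say so: 6.2.3 defines no onset day, and Table JAIY.6.7 lists no such analysis. The point concerns how a run of daily p-values would be read.

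Nor is a single multiple, such as three times the nominal rate, supportable. The multiple depends on early itch rates that the documents do not give, and on the test. The log-rank figures are the higher ones, yet log-rank is only the SAP's fallback. The Cox figures are lower and omit the planned covariates. The scenario also needs a wholly ineffective dose beside a strong one, whereas Protocol 5.5 reports benefit for both doses in Phase 2. If the weaker dose has some effect, its early significant day is not a false positive.

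What survives is the rule itself. A statement that nothing is adjusted does not tell the reader that one dose's early p-value was reached only because the other dose succeeded. An unequal pair is also plausible: Protocol 5.5 says 4 mg appeared to act faster than 2 mg on the stringent skin endpoints.

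**Conclusion.** The concern holds as a defect in an exploratory stopping rule. When the other dose is strong, a dose with no effect shows a false significant day about 1.4 to 4.4 times as often as the nominal 5% (7%/5% by Cox Wald at the low end, 22%/5% by log-rank at the high end). At HR 2 the range is about 5% to 15%, or 1 to 3 times. With both doses ineffective there is almost no inflation. About half of the false days would be read as benefit; the rest favour placebo.

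These sizes rest on the assumed response rates, hazard ratios and 90 or 100 analysable patients per arm. The mechanism rests on the SAP text alone. The family-wise error rate and the controlled itch tests are unaffected. The change is a cheap improvement worth making.

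**What to change.** Replace the shared gate in SAP 6.2.3 with a dose-specific one, for example:

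*For each baricitinib dose separately, if the comparison with placebo is significant at Day k, that dose is tested at Day k−1; testing of that dose stops at its first non-significant day.*

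The cost is one sentence. No alpha split, new data or extra model is needed. The downside is that a dose not significant by Day 14 that had separated earlier gets no formal earlier-day test in this analysis; its curves and daily response rates can still be shown descriptively.

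The change does not reach the restricted mean survival time comparisons at Days 2 to 5 in the same section, which have no stated gate and remain unadjusted exploratory results.
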